3.11 Saliva Test Protocol

3.11.1 Saliva Collection

The saliva collection tool should be about 20 mL in length and in a conical shape polypropylene tubes. An amount of 1 – 2 mL saliva sample will be collected during assessment by the Main Researcher via ‘passive drool’ method and initially stored at –20°C after collection in an insulated cooler box with reusable ice packs. The Main Researcher will transport the biospecimen to the Biotechnology Research Institute (BRI), Universiti Malaysia Sabah (UMS). Upon arrival to the lab, it should be stored at –80 °C until analysis is done (Paulino YC et al., 2020).

3.11.2 Sample Preparation

At the lab, a 100 µL aliquot of thawed saliva will be mixed with 10 µL of internal standard (IS) solution and 100 µL of acetonitrile in a 1.5 ml microcentrifuge tube. Then it will be vortexed at high speed to precipitate the BQ proteins. The mixture will then be diluted with 800 µL of 0.1% formic acid in MeOH: H₂O (v:v = 1:1) and then later centrifuged at 13,500 x g for 5 min. The resultant supernatant will be transferred to High Performance Liquid Chromatography (HPLC) vials and subjected to Liquid Chromatography–Mass Spectrometry (LCMS) analysis (Franke AA et al,2015).

3.11.3 Chemicals

Arecoline hydrobromide, guvacine hydrochloride, nicotine, cotinine, hydroxycotinine, NNN, NAT, NNK, 4-(Methyl-d₃-nitrosamino)-1-(3-pyridyl)-1-butanone (NNK-d₃), nicotine-d₄, cotinine-d₃ and eugenol and o-eugenol will be purchased from Sigma-Aldrich (St. Louis MO), whereas Guvacoline hydrobromide, N-nitrosoguvacoline, Arecaidine Hydrobromide, Arecodine-d₅, hydrobromide salt will be purchased from Medical Isotopes (Pelham, NH). All

solvents will be confirmed of LCMS grade and will be purchased from Fisher Scientific (Waltham MA) (Franke AA et al,2015).

3.11.4 Standards

The standard stock solutions of arecaidine, arecoline, guvacoline, guvacine, nicotine, cotinine, hydroxycotinine, N-nitrosoguvacoline, NNK, NNN, NAT, eugenol, and o-eugenol will be prepared in MeOH at concentrations of 10 µg/mL. The IS solution consisting of arecoline-d5, nicotine-d4, cotinine-d3, NNK-d3 will be prepared in MeOH at concentrations of 10 µg/mL.

The calibrator solutions will be made by mixing 100 µL standard stock solutions with 10 µL IS solution and 900 µL 0.1% formic acid in MeOH:H₂O (1:1). Calibration curves will be generated by serially diluting standard stock solutions in 0.1% formic acid in MeOH:H₂O (1:1) to obtain working concentrations of 0.1, 1, 10, 100, 200, 500, 1000, and 5000 ng/mL (Franke AA et al,2015).

3.11.5 LCMS analysis

The lab test will be run by staff at the Biotechnology Research Institute (BRI), Universiti Malaysia Sabah (UMS). The BRI lab is located at Kota Kinabalu, Sabah which is about 1 to 1.5 hours from the study site and precaution will be taken to deliver samples within 8 hours after collection due to the quick disappearance property of areca nut biomarkers after 8 hours of collection.

LCMS analysis will be carried out on a model Accela ultra HPLC system coupled to a Q Exactive Orbitrap Mass Spectrometer and a CTC PAL autosampler (all from Thermo-

Fisher, San Jose, CA). 10 µl of the above mixture will be injected into a Kinetex C18 column (150 x 3 mm, 2.6 µm, Phenomenex, Torrance CA) with a Phenomenex UHPLC C18 pre-column (3.0 mm i.d.).

Gradient elution will be performed at a flow rate of 300 µL /min using 10 mM ammonium hydroxide in H₂O (A) and 10 mM ammonium hydroxide in MeOH (B) as follows: 0-15.0 min linear gradient from 65%A to 20%A; 15.0-20.0 min hold at 20%A; 20.0-20.1 min increase to 65%A then to equilibrate it for 5 minutes. Total HPLC time including equilibration will be around 25 minutes.

Mass analysis will be performed under positive and negative electrospray full scan mode, the conditions will be as follows: (+) ESI spray voltage 4.5 kv, capillary transfer temperature 350 °C, (-) ESI spray voltage 3.5 kv, capillary temperature 320 °C; and other parameters will be: HESI heater temperature 200 °C, sheath gas flow rate 30 unit; auxiliary gas 5 unit, in-source CID 5 ev, scan range 100 ~ 1000. AGC target 1e6, maximum injection time 100 ms, resolution 35,000, microscan 1.

Quantitation of all analytes will be performed with Xcalibur™ software by extracting the within 5 ppm of the calculated exact masses as according: Arecoline and Arecoline-d5 at +ESI [M+H]⁺ 156.10191 and 161.13329; Guvacoline at +ESI [M+H]⁺ 142.08626, Guvacine at +ESI [M+H]⁺ 128.07061, Arecaidine at +ESI [M+H]⁺ 142.086, NNN at +ESI [M+H]⁺ 178.09749, NAT at +ESI [M+H]⁺ 190.09749, NNK and NNK-d3 at +ESI [M+H]⁺ 208.10805 and 211.12688, Nicotine and Nicotine-d4 at +ESI [M+H]⁺ 163.12297 and 167.14808, Cotinine and Cotinine-d3 at +ESI [M+H]⁺ 177.10224 and 180.12107, N-nitrosoguvacoline at +ESI [M+H]⁺ 171.07642, Hydroxycotinine at +ESI [M+H]⁺ 193.09715, and chavibetol at -ESI [M-H]⁻ 163.07590 (Franke AA et al,2015).

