Franke AA et al., in 2016 conducted a pilot study to further explore the pharmacokinetics of AN's alkaloid as those assessment of biomarkers was very in need to evaluate the effectiveness of BQ cessation program that was targeted to reduce the oral cancer burden in the high-risk areas in Hawaii. The study found that AN alkaloids; **arecoline, guvacoline, guvacine, and arecaidine were detected in saliva of all participants and peaked within the first 2 hours post-chewing before returning to baseline levels after 8 hours**. The salivary chavibetol was reported in participants consuming betel leaves in their quid and it peaked 1-hour post-chewing. Thus, the study concluded the AN biomarkers from saliva can be followed up only on a short-term basis (≤ 8 h post-chewing). The study too claimed to find similar AN alkaloids from urine samples of the participants.

Franke AA et al. (2022) reported that **saliva bio verification results are valid to be used to verify the self-reported chewing status of participants ('quitter' or 'chewer') at day 22 follow-up to evaluate cessation program's effectiveness**. In the BENIT trial, among the quitters, the decrease in AN compounds were most significant for arecoline ($p=0.044$), followed by arecaidine ($p=0.042$) and nicotine ($p=0.011$). Among the current chewers, the significant decrease was noted only for hydroxycotinine ($p=0.004$).

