The subjects will be assigned into a group of seven participants and the appointments for each group participants will be given across the week. A total of 2 group sessions will be made in a day; a morning session and an afternoon session. Participants will be sought of their preferred time to increase participation in the intervention group.

[figure not shown]

Figure 3.7 Flow of Participants on the Screening of the study (Day 0)

1st Session (Day 1)

On the **1st session of the intervention (Day 1)**, attendance of all eligible and consented participants will be taken at **Checkpoint 1** and the nature of intervention will be introduced through a **brief talk**. The information that the participants will undergo 5 sessions of support and information group designed to assist them to quit BQ chewing habit over 22 days period will be emphasized and they will be reminded that their continuous commitment to the intervention is utmost important to their future cessation.

They will also be briefed that each support session will consume approximately 1-2 hours. It will be conducted by the main researcher in Malay language (Bahasa Melayu) and

translated by trained facilitators into Bajau language verbally. A translation script will be prepared before initiation of the intervention for standardization to minimise bias or any poor explanation in Bajau language.

After the brief introduction, an **educational talk** will be delivered to the study participants by the main researcher. The content of the talk will be based on the topics of the educational booklets (general information regarding AN and BQ, risk associated with BQ chewing behaviour through projection of captivating graphical aids, cessation strategies that are modeled after tobacco cessation and researcher's contact information) but in a more detailed and interactive manner. An aid of Microsoft Powerpoint multimedia presentation will be used. A two-way communication mode will try to be sought throughout the entire talk. Participants will be encouraged to participate actively during the educational talk session. The aim of the educational talk is to increase the chewer's awareness, motivation and to enhance their commitment to cease behaviour. Participants too will be encouraged to share their experience and their feelings of chewing BQ and what are the challenges they face while practicing this habit.

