3.14 Data Collection

3.14.1 Baseline

The facilitators from the Kota Belud Dental Clinic staff will be trained and standardised for the conduct of this study. A training manual will be given to each facilitators. They will be briefed and their understanding on every item of the questionnaire and worksheets will be scrutinised and refined as intended by the study. Any difficult words identified by the facilitators will be changed to a simpler alternative. Translated words into Bajau dialect will be discussed and decided upon for standardisation.

From face-to-face interviews with the participants, information regarding demographics details and baseline information about BQ chewing behaviour, BQ composition, BQ dependency levels, reasons for chewing and readiness and self-perceived barriers to quit will be garnered. Face-to-face interview mode was chosen as a method to complete the questionnaire to obtain a better response rate and to minimise inaccurate response due to illiteracy issues and participant's poor comprehension due to age.

Participant's baseline saliva samples will be gained for biomarker comparison as a method to verify the intervention's self-reported effectiveness. Saliva samples collected will be transported within 2-3 hours to the lab facilities to be stored under -80 °C temperature. The transportation of these saliva samples will be monitored and carried out by the main researcher.

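### Section 3.11.5 turns an 8-hour detection window since chewing into an 8-hour delivery limit since collection; transport limits must be reconciled and a clear saliva result read as recent abstinence only

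*Protocol*

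**What the plan says.** Section 2.11 summarises a pharmacokinetic pilot study in which salivary areca alkaloids "peaked within the first 2 hours post-chewing before returning to baseline levels after 8 hours". The protocol concludes from it that these biomarkers "can be followed up only on a short-term basis (≤ 8 h post-chewing").

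Section 3.11.5 places the laboratory "about 1 to 1.5 hours from the study site" and says that "precaution will be taken to deliver samples within 8 hours after collection", the reason being "due to the quick disappearance property of areca nut biomarkers after 8 hours of collection". No source is attached to that sentence.

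Section 3.14.1 (Baseline) says: "Saliva samples collected will be transported within 2-3 hours to the lab facilities", for storage at -80 °C. Section 3.14.2 (day 22) and Section 3.14.3 (months 1 and 3) give no transport time. Under Section 3.11.1, samples are "initially stored at –20°C after collection in an insulated cooler box with reusable ice packs" until they reach the laboratory.

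Sections 3.12.2 and 3.14.2 treat a level above the cut-off as evidence that the habit has not ceased. Section 3.14.3 goes further and uses the same cut-offs to represent cessation. Both follow-up sections say that the saliva result serves to verify self-report. Section 3.8 admits people with as few as two to three chewing episodes a week.

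**The concern.** The 8 hours in Section 2.11 and the 8 hours in Section 3.11.5 run on different clocks. The first starts at the chew and ends when the mouth has cleared. The second starts when saliva enters the tube. The stated reason for the delivery rule therefore appears to be a property of the mouth applied to a stored sample.

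Two things are at stake. The field team has two maximum times for one step, and the shorter one is written for one visit only. More importantly, once the 8 hours is read as a transport matter, prompt delivery seems to deal with it. It does not. The interval that limits what the assay can detect is the time from last chew to collection, and the plan neither records that interval nor uses it when interpreting the result.

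**Working it through.** No power, alpha or sample size figure is involved. The check compares the time limits and then asks what each can protect.

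**1. The limits side by side**

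| Protocol section | Limit | Clock starts at | Applies to |
|---|---|---|---|
| 2.11 | 8 h | chewing | detectability in the mouth |
| 3.11.5 | 8 h | collection | delivery to the laboratory, no visit named |
| 3.14.1 | 2-3 h | collection, as the text implies | transport to -80 °C storage, Baseline |
| 3.14.2, 3.14.3 | none | not applicable | day 22, months 1 and 3 |

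Section 3.11.5 cites nothing for its 8 hours. That the figure came from the pilot study is an inference, but Section 2.11 is the only other place that gives an 8-hour figure for these biomarkers. No section reports how stable they are in collected saliva.

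**2. Size of the difference between the transport limits**

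- Ratio: 8/3 = 2.7 and 8/2 = 4.
- Holding time left after a drive of 1 to 1.5 h, under Section 3.11.5: 8 - 1.5 = 6.5 h to 8 - 1 = 7 h.
- Holding time left under Section 3.14.1: 2 - 1.5 = 0.5 h to 3 - 1 = 2 h.

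The shorter limit can be met with the stated drive.

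**3. Why transport time cannot stand in for time since chewing**

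Let *a* be the hours from last chew to collection and *b* the hours from collection to -80 °C. Section 2.11 concerns *a*. Sections 3.11.5 and 3.14.1 restrict *b*. Take an assumed participant with *a* = 24 h and *b* = 2 h. The sample satisfies both transport rules, yet it was taken 24 - 8 = 16 h after the detection window closed.

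**4. How often this could matter for the lightest eligible chewers**

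Assume that each episode opens one 8-hour window, that windows do not overlap, and that the visit time is unrelated to chewing. A week has 7 × 24 = 168 h.

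- Three episodes a week: 3 × 8 = 24 h covered, and 24/168 = 14%.
- Two episodes a week: 2 × 8 = 16 h covered, and 16/168 = 10%.

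On these assumptions a continuing chewer at the eligibility minimum is outside the window for about 86% to 90% of the week. This illustrates the lower end of eligibility. It is not an estimate for the sample: people who chew throughout the day would usually be inside the window. The return to baseline in Section 2.11 is also not stated to mean below the cut-offs of Section 3.12.2, so 8 hours is approximate.

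**5. Whether the plan captures the missing interval**

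The follow-up questionnaire (Appendix M) asks for chewing status, frequency, quids per day and ingredients. It does not ask when the participant last chewed.

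**The case against.** The two transport limits are compatible: a sample delivered in 2-3 hours also meets the 8-hour bound. This stands. The defect is two ceilings for one step, the longer resting on an unsupported reason.

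A reader might infer that alkaloids are lost in the tube, that loss reads as cessation, and that it falls unevenly by arm because intervention groups meet twice a day ("A total of 2 group sessions will be made in a day; a morning session and an afternoon session"). The documents do not support this. They report no loss in collected saliva, and they specify -20 °C storage in a cooler box before the laboratory. The pattern also does not line up by visit. The 2-3 hour rule is written for Baseline, when saliva is taken on the screening day before the groups begin. The group timetable coincides with saliva collection only at day 22, where 2-3 hours is not written. No group structure is given for the 3-month saliva visit.

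A reader might also infer that an 8-hour limit permits complete loss. Section 3.11.5 speaks of disappearance after 8 hours, so delivery within 8 hours would precede it on the protocol's own wording.

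Finally, Section 2.11 cites a BENIT report that saliva is valid for verifying self-reported status at day 22. That supports using saliva as corroboration. The results quoted from it are falls in compound levels among quitters and among chewers. They do not show how often an infrequent chewer sampled beyond 8 hours would be detected.

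**Conclusion.** The concern holds as a wrong stated premise with a consequence for interpretation. Section 3.11.5 counts 8 hours from collection, while the protocol's own evidence counts them from chewing. Two transport limits, differing by a factor of 2.7 to 4, are written for one step, and only the longer one reaches the two follow-up visits at which saliva is used to verify self-report. Sections 2.11, 3.11.5 and 3.14.1 must be reconciled.

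On the protocol's reported pharmacokinetics, a below-cut-off areca alkaloid result supports no chewing in about the last 8 hours. It does not by itself verify cessation. How many participants this affects depends on the mix of chewing frequencies, which the protocol does not give. The reading does not extend to cotinine, for which Section 2.11 gives no such window.

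The point is of moderate weight: saliva is a secondary outcome, and the primary outcome in Section 3.12.1 is self-reported quitting.

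**What to change.** 1. In Section 3.11.5, delete the 8-hour delivery limit and its reason.
2. State one transport limit for baseline, day 22 and month 3, in both arms. The protocol's own 2-3 hours is workable with the stated drive. It too has no stability source in the protocol, so its merit is that it is the shorter of the two and feasible. A longer limit would need a cited stability result for stored saliva.
3. Log the collection time and the time each sample enters -80 °C storage, so that late samples can be identified.
4. At each saliva collection, record hours since last chew.
5. In Sections 3.12.2, 3.14.2 and 3.14.3, describe a below-cut-off areca alkaloid result as no chewing in about the last 8 hours, consistent with self-report but not verification of cessation. Treat cotinine separately.

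The cost is three time fields per sample, edits to the sections named, and possibly a second drive when two groups give saliva on the same day. That drive falls to the main researcher, whom Sections 3.11.1 and 3.14.1 name as the person transporting samples. The trial also accepts a weaker claim of biochemical verification for a secondary outcome.

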3.12 Outcome of the Study

3.12.1 Primary Outcome Measures

Change in the number of participants who self-reported that they had quit BQ chewing will be measured through follow-up questionnaire at day 22. This will represent the short-term cessation prevalence achieved by the study.

Change in the number of participants who self-reported that they had quit BQ chewing will be measured through follow-up questionnaire at Month-3. This will represent the intermediate-term cessation prevalence (stay-quit) achieved by the study.

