1.6 Aim and Objectives

1.6.1 Aim of the study

The aim of this study is to cross culturally adapt a BQ cessation program for a Malaysian high-risk community and evaluate the effectiveness of the adapted BQ cessation program using a combination of self-reported cessation rates and salivary biomarkers measurements.

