1.8 Rationale of the Study

Firstly, since there is an **established BQ cessation program** with at least 5 years of implementation (Moss J et al., 2015), Malaysia can tap into the essentials of this program for the BQ users in this country. As the structure of the cessation program was modeled after a group-based smoking cessation program, this structure resembles the '*Kesihatan Oral Tanpa Amalan Rokok*' (KOTAK) program that is currently being held nationwide by the government dentist. Due to the **familiarity of the intervention structure**, this intervention can be easily utilised by the Malaysian dentist as all dentists were adequately trained under the KOTAK cigarette-smoking cessation program.

Secondly, the concept and framework of **Cognitive Behavioral Therapy (CBT) has yielded a high success rate**. Raja M. (2014) claimed a CBT based group cessation yielded more success rate compared to control group which only educated BQ chewers with a Basic Health Education model. Moss J et al. (2015) who utilised a CBT program too reported the study yielded a surprising 65% of self reported cessation rate among the study participants. The

cognitive component of the program that addresses the chewer's attitude and beliefs and the **behavioural component** that aims to replace chewing-promoting behaviours with behaviours conducive for quitting **is a very advantageous and comprehensive intervention.**

Thirdly, this **model of the therapy is flexible** as it can accommodate a **social component** to **increase the sustainability of cessation program in a community** by educating and empowering the participant's community (eg. the villagers of chewers). Another benefit from the CBT program is that the participants possessed a higher degree of motivation to quit and experienced lower withdrawal symptoms post quitting (Schnoll RA, 2005). A study stated that **without any interventional program, BQ chewers face difficulty in quitting** their ill behaviour due to the dependency syndrome.

Fourthly, with the **advent of liquid chromatography-mass spectrometry (LC-MS)** technology, the appearance and disappearance of betel alkaloids (biomarkers) can be measured. Thus, the **effectiveness of the cessation program can be tested** to validate the true abstinence of participants to BQ chewing from the cessation program (Frankie AA, 2016 & 2022).

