3.12.2 Secondary Outcome Measures

Levels of areca nut biomarkers in saliva samples will be tested via liquid chromatography mass spectrometry at day 22. The cut-off levels for areca nut biomarkers are arecoline (60 ng/mL), arecaidine (10 ng/mL), guvacoline (20 ng/mL), and guvacine (6 ng/mL) and cotinine (10 ng/mL). Biomarkers level above this cut-off points represent that participants are still practicing the habit and have not ceased the habit.

Levels of areca nut biomarkers in saliva samples will be tested via liquid chromatography mass spectrometry at Month-3. The cut-off levels for areca nut biomarkers are arecoline (60 ng/mL), arecaidine (10 ng/mL), guvacoline (20 ng/mL), and guvacine (6 ng/mL) and cotinine (10 ng/mL). Biomarkers level above this cut-off points represent that participants are still practicing the habit and have not ceased the habit.

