3.14.2 Follow up at 22-day (short term)

Information regarding participant's personal particular, participant's compliance, current chewing status, number of cut-down of habit by the participants (quid/day), total number of session attended and reasons if absent and the BQ composition if participants are still chewing will be gained through a face-to-face interview with a follow-up questionnaire.

Participant's 22-day saliva samples will be gained to evaluate the short term effectiveness of the intervention and to verify the self-reported outcomes. The levels of areca nut and cotinine biomarkers in saliva samples (via liquid chromatography mass spectrometry) will be evaluated. The cut-off levels for areca nut biomarkers are arecoline (60 ng/mL), arecaidine (10 ng/mL), guvacoline (20 ng/mL), and guvacine (6 ng/mL) and the cut-off levels for cotinine levels (10 ng/mL). Biomarkers level above this cut-off points represent that participants have still not ceased the habit.

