3.14.3 Follow up at 1-month and 3-month

Information regarding participant's personal particulars, participant's current chewing status, number of cut-down of habit by the participants (quid/day) and the BQ composition if participants are still chewing will be taken through face-to-face interview with a follow-up questionnaire.

At 3-month, participants' saliva samples will be collected to evaluate the intermediate term effectiveness of the intervention and to verify the self-reported outcomes. The same cut-off levels of AN and cotinine will be used to represent the participant's cessation of their chewing habit.

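### Saliva is collected to verify self-reported quitting, but no rule says what happens to the primary quit count when a participant's saliva contradicts the report

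*Protocol*

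**What the plan says.** Protocol 3.12.1 sets two primary outcomes, both taken from the follow-up questionnaire. The short-term one is "Change in the number of participants who self-reported that they had quit BQ chewing will be measured through follow-up questionnaire at day 22" and the intermediate one is "Change in the number of participants who self-reported that they had quit BQ chewing will be measured through follow-up questionnaire at Month-3". The questionnaire in Appendix M obtains this from a single item on current chewing status.

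Section 3.12.2 makes salivary biomarker levels at the same two visits a separate secondary outcome. The cut-offs are arecoline 60, arecaidine 10, guvacoline 20, guvacine 6 and cotinine 10 ng/mL, and the section states: "Biomarkers level above this cut-off points represent that participants are still practicing the habit and have not ceased the habit".

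Elsewhere the saliva is given a checking role:
- 1.8, rationale for the assay: "to validate the true abstinence of participants to BQ chewing from the cessation program".
- 3.14.1, baseline: "Participant's baseline saliva samples will be gained for biomarker comparison as a method to verify the intervention's self-reported effectiveness".
- 3.14.2, Day 22: "to evaluate the short term effectiveness of the intervention and to verify the self-reported outcomes".
- 3.14.3, Month 3: "to evaluate the intermediate term effectiveness of the intervention and to verify the self-reported outcomes". This section adds that the same cut-offs will represent cessation.

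The aim in 1.6.1 is to evaluate effectiveness "using a combination of self-reported cessation rates and salivary biomarkers measurements". Objective iv in 1.6.2 lists self-report and biomarkers as items (a) and (b).

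**The concern.** A check is useful only if a failed check has a consequence. Here the protocol states the purpose of the saliva (to verify the reports) and the meaning of a positive result (the person has not stopped). It then fixes the primary outcome so that a positive result has no effect on it. A participant who answers that the habit has stopped, while that visit's saliva shows arecoline above 60 ng/mL, remains a quitter in the primary count.

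This matters because the arms differ in their exposure to pressure to report success. The intervention arm has five group sessions, a shared quit day and a monetary incentive for each session attended. Its Day 22 questionnaire is completed at the fifth session. Trained facilitators who assist with the sessions also serve as questionnaire interviewers (3.10.2.3), and follow-up is face to face. The control arm receives a booklet. If more continuing chewers claim to have quit in the intervention arm than in the control arm, the self-reported difference is biased towards the intervention. Samples that could expose part of this will already be in hand for both arms.

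**Working it through.** **Step 1: one participant, one visit, both definitions.** Take a participant who reports having stopped and whose saliva is above a cut-off.

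| Source | Status of this participant |
|---|---|
| 3.12.1, primary outcome | Quitter |
| 3.12.2, secondary outcome | Has not ceased |
| 3.14.2 and 3.14.3 | Report is to be verified by saliva; no consequence stated |

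No other section reclassifies this person or says which status prevails. The gap does not depend on any calculation. The rest only shows how much it could matter.

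**Step 2: the plan's own figure.** Section 3.4 gives 38.64% versus 9.09%, alpha 0.05, power 0.80 and 1:1 allocation. It does not state sidedness; two-sided reproduces the total.
- d = 0.2955, mean proportion p̄ = 0.23865.
- n₀ = [1.960·√(2·p̄·(1−p̄)) + 0.842·√(p₁(1−p₁) + p₂(1−p₂))]² / d² = 31.46.
- With continuity correction: n = (n₀/4)·[1 + √(1 + 4/(n₀·d))]² = 37.9, so 38 per arm and 76 in total, as stated.

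**Step 3: chance of a false positive.** The documents give no misreporting rate, so these rates are assumptions. Suppose true quitting is 9.09% in both arms, controls report correctly, and a share f of continuing intervention-arm chewers claims to have quit. The reported intervention rate is 0.0909 + 0.9091·f. The chance of a significant result favouring the intervention is Φ[(d − 1.960·se₀)/se₁], with se₀ the pooled and se₁ the unpooled standard error at 38 per arm, ignoring clustering and continuity correction.

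| f | Reported rates | Chance of false positive |
|---|---|---|
| 0 | 9.1% vs 9.1% | 0.025 |
| 5% | 13.6% vs 9.1% | 0.09 |
| 10% | 18.2% vs 9.1% | 0.21 |
| 20% | 27.3% vs 9.1% | 0.54 |

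Worked case, f = 10%: d = 0.0909, se₀ = 0.0787, se₁ = 0.0780, so (0.0909 − 0.1543)/0.0780 = −0.81 and Φ = 0.21.

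**Step 4: what a stricter count costs.** Suppose the rates in 3.4 are self-reported and a share g of self-reported quitters in both arms fails the saliva test. Both rates are multiplied by (1 − g), and the formulas above are reapplied.

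| g | Rates | Power at 38 per arm | n per arm for 80% power |
|---|---|---|---|
| 0 | 38.6% vs 9.1% | 0.87 | 38 |
| 10% | 34.8% vs 8.2% | 0.82 | 44 |
| 20% | 30.9% vs 7.3% | 0.76 | 51 |
| 30% | 27.0% vs 6.4% | 0.68 | 60 |

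Power starts at 0.87, not 0.80, because the power column has no continuity correction while the 38 and the last column do.

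**The case against.** The strongest reply is that the protocol does what it set out to do. A reader might infer from 1.6.1 that the outcomes contradict the aim. They do not clearly do so: objective iv lists self-report and biomarkers as two items, 3.12.1 and 3.12.2 match them one to one, and a combination can simply mean that both are measured. A reader might also infer that the saliva yields no cessation status at all. That goes too far as well, since 3.14.3 uses the cut-offs to represent cessation. Both corrections stand. What they leave untouched is that the two statuses are never brought together for a participant.

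A second reply is that discordant cases can be handled in a statistical analysis plan, which is not at hand. Such a plan could add a tabulation or sensitivity analysis. It could not change the primary count without departing from 3.12.1, which fixes that count as self-report.

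A third reply is that saliva is a weak arbiter. Section 2.11 limits the areca markers to 8 hours or less after chewing, and 3.8 admits people who chew as little as two to three times a week, so many continuing chewers could test negative. This stands. It rules out treating a negative sample as proof of quitting, least of all of the sustained quitting intended at Month 3. It does not weaken a positive sample, which under 3.12.2 means the habit continues.

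Finally, the misreporting rates are assumed and deliberately one-sided. Participants in both arms know they will give saliva, which may restrain false claims, and the incentives reward attendance, not a claim of quitting.

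**Conclusion.** The concern holds in a limited form. Sections 1.8 and 3.14 say that saliva verifies self-report, and 3.12.2 says what a positive result means. Yet 3.12.1 counts every reported quit and nothing resolves a disagreement, so the primary quit count is unverified self-report whatever the assays show. This follows from the text alone.

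Its numerical effect is unknown. The rise in false-positive risk from 0.025 to about 0.09, 0.21 and 0.54 assumes no true effect, misreporting of 5%, 10% and 20% confined to intervention-arm chewers, 38 per arm and no clustering. Given the 8-hour window, a saliva rule would remove only part of such a bias.

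It is tempting to add misreporting to the planned 38.64% and 9.09% and quote an inflated treatment effect. The documents do not support this, because 3.4 does not say whether those rates are self-reported or verified; if they are self-reported, misreporting would be counted twice.

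**What to change.** In 3.12, add a per-person outcome at Day 22 and Month 3: a participant who reports having quit, but whose saliva at that visit has any one of arecoline, arecaidine, guvacoline or guvacine above its stated cut-off, is counted as a chewer. Leave cotinine out of this rule. Smoking is recorded at baseline and is not an exclusion, so an abstinent chewer who smokes could be misclassified.

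Name the outcome *self-reported quit not contradicted by saliva*, not *verified quit*, and cite the 8-hour window as the reason. Report it beside the self-reported rate, with the number of discordant participants and the number with missing saliva in each arm. State that saliva-verified effectiveness under objective iv will not be claimed from the self-reported rate alone.

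No new samples or assays are needed, since both arms already give saliva at both visits. The cost is lower quit rates and possibly lower power. If the rates in 3.4 are self-reported and 10% to 30% of self-reported quitters in both arms fail the test (an assumed range), power at 38 per arm falls from about 0.87 to between 0.82 and 0.68, before any allowance for clustering. Section 3.4 should therefore state which kind of rate it uses, and the rule should be settled before data collection.
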